6.1 Unscheduled Visits

During the conduct of the study, there are multiple situations that may require the subject to come to the research site for an unscheduled visit. Reasons for an unscheduled visit include but are not limited to the following:

- Subject missed the visit window
- Subject experienced an AE and needed to be seen for follow-up
- Due to lab results, the investigator has determined that for the welfare of the subject, she or he should be seen sooner than previously scheduled

The data from these visits will be recorded just as any study visit.

6.2. Subject Withdrawal from the Study

Subjects may withdraw consent for the study at any time for any reason without impact to their care. In addition, a subject may be withdrawn by the investigator or the sponsor if enrollment in the study is inappropriate, lack of adherence to the intervention or study procedures or visit schedules, the study plan is violated, or for administrative and/or other safety reasons. It is documented whether or not each subject completes the clinical study. If the subject actively withdraws consent for collection of follow-up data (i.e., subsequent anticancer treatments, safety follow-up, and survival), then no additional data collection occurs; however, all subjects are informed of the option to discontinue treatment and/or study assessments but allow collection of information in the follow-up period of the study. In the event that the latter occurs, the end-of-treatment (EOT) visit should be conducted (see **Table 8** and **Table 9** for EOT visit procedures). Thereafter, the subject will return for follow-up visits for safety and disease/survival status, with procedures as outlined above in **Table 10**.

If a subject withdraws from the study and has not yet received a dose of study drug, that subject is replaced according to the procedure outlined in **Section 3.2; Replacement of Subjects**.

7 STUDY EVALUATIONS AND MEASUREMENTS

7.1 Demographic and Medical Record Review

The following variables will be collected at screening and abstracted from the electronic medical chart:

- Date of birth
- Height
- Weight
- Medical History, Prior and Concomitant Medications, and Allergies
 - All concomitant medications must be recorded, and any medication received within 30 days before screening must be recorded.
 - Concomitant medications include any prescription, over-the-counter, or natural/herbal preparations taken or administered during the study period.
- Karnofsky Performance Status, as defined in **Table 11**:

Table 11. KARNOFSKY PS
100—Normal, no complaints; no evidence of disease
90—Able to carry on normal activity; minor signs or symptoms of disease
80—Normal activity with effort, some signs or symptoms of disease
70—Cares for self but unable to carry on normal activity or to do active work
60—Requires occasional assistance but is able to care for most of personal needs
50—Requires considerable assistance and frequent medical care
40—Disabled; requires special care and assistance
30—Severely disabled; hospitalization is indicated although death not imminent
20—Very ill; hospitalization and active supportive care necessary
10—Moribund
0—Dead

7.2 Physical Assessment

Physical assessments will be performed according to the assessment schedules.

Full physical assessments will include assessments of the head, eyes, ears, nose, and throat and the respiratory, cardiovascular, gastrointestinal, musculoskeletal (including spine and extremities), neurological, dermatological, hematologic/lymphatic, and endocrine systems. Height will be measured at Screening only. Targeted physical assessments are to be utilized by the investigator and/or research nurse on the basis of clinical observations and symptomatology. Clinically notable abnormalities that are considered clinically significant in the judgement of the investigator are to be reported as AEs.

7.3 Vital Signs

Height will be assessed at screening only. Weight will be assessed according to the Study Schedule (**Tables 8 and 9**) and as clinically indicated at any other time.

Vital signs (BP, pulse, temperature, and respiratory rate) will be evaluated according to the assessment schedules (**Table 8 and Table 9**). Any changes in vital signs should be recorded as an AE, if applicable. Body temperature: Body temperature will be measured in degrees Celsius at the times indicated in the Study Schedule (**Table 8 and Table 9**).

On infusion days, subjects will be monitored during and after infusion of each investigational product(s) as presented in the bulleted list below. Supine BP will be measured using a semi-automatic BP recording device with an appropriate cuff size, after the subject has rested for at

least 5-10 minutes. BP and pulse will be collected from subjects before, during, and after each infusion at the following times (based on a 60-minute infusion):

- Prior to the beginning of the infusion (measured once from approximately 30 minutes before up to 0 minutes [ie, the beginning of the infusion])
- Approximately 30 minutes during 60-minute infusions (halfway through infusion). Vitals should be obtained at approximately 15 minutes during subsequent 30-minute infusions (halfway through infusion).
- At the end of the infusion (approximately 60 or 30 minutes \pm 5 minutes)
- A 1-hour observation period is recommended after the INCMGA00012 infusion prior to beginning the INCAGN01876 infusion.

7.4 *Electrocardiogram (ECG)*

A 12-lead electrocardiogram will be performed at screening only.

7.5 *Clinical Laboratory Evaluations*

Blood sampling will be performed for the following laboratory evaluations (**Table 12**) according to the schedule outlined in **Table 8 and Table 9**:

- Hematology
- Chemistry and Liver Function
- Additional electrolytes
- Endocrine
- Hepatitis screening
- Urinalysis

Category	Tests
Hematology	RBC, hemoglobin, hematocrit, platelet count, WBC with differential
Chemistry and Liver function tests (comprehensive metabolic panel)	Basic metabolic panel, LDH, AST, ALT, total Bilirubin (with direct and indirect components), alkaline phosphatase
Additional electrolytes	Magnesium, phosphorus
Endocrine	TSH, free T4
Hepatitis screening	HBV surface antigen (HBsAg), HCV viral load (RNA quant)
Urine	Microscopic Urinalysis

7.6 *Pregnancy Testing*

WOCBP are required to have a urine or serum pregnancy test performed during screening and this test must be completed within 7 days before the first dose of study drug. WOCBP must exhibit a negative serum or urine pregnancy (minimum sensitivity 25 IU/L or equivalent units of HCG) within 7 days prior to the start of study drug. Pregnancy testing will be performed as outlined in **Table 8 and Table 9**; this includes the EOT visit, although a pregnancy test is not

required if a subject is going to hospice. Urine pregnancy tests will be conducted during the intervention phase of the study only as medically indicated. If a urine pregnancy test is positive or cannot be confirmed as negative, the results should be confirmed with a serum pregnancy test. If the serum pregnancy test is negative after a urine test was positive, the investigator will assess the potential benefit/risk to the subject and determine whether it is in the subject's best interest to resume study drug and continue participation in the study. A serum pregnancy test should also be repeated at the EOT visit.

7.7 Efficacy Evaluations

7.7.1. Anti-Tumor Effect Definitions

Modified Response Assessment in Neuro-Oncology (RANO) criteria ([Ellingson et al, Neurotherapeutics 2017](#)) will be used to assess for tumor response and progression, with definitions as outlined below. Radiologic response will be assessed by comparing the pretreatment baseline and on-treatment MRI scans. Radiologic progression will be determined by using the smallest tumor measurement at either the pretreatment baseline or after initiation of study medication. MRI scans will be performed no less frequently than every 8 weeks. The MRI scan should be performed within 7 days prior to a cycle start (and ideally within 3 days prior). Adjustments to this 7 day window are allowable per the treating physician's discretion; however restaging scans MUST BE performed and reviewed before the subsequent cycle's dose may be initiated. MRIs will be interpreted by the attending neuro-radiologist at the University of Pennsylvania assigned as a sub-investigator on this study.

Measurable disease should be defined as contrast enhancing lesions with a minimum size of *both* perpendicular measurements greater than or equal to 10mm. For example, if the largest diameter is 15 mm but the perpendicular diameter is 8 mm, this would constitute *non-measurable disease*. Up to a total of five target measurable lesions should be defined and ranked from largest to smallest. Non-measurable disease should be defined as lesions that are too small to be measured (less than 1 cm in both perpendicular dimensions), lesions that lack contrast enhancement (non-enhancing disease), or lesions that contain a poorly defined margin that cannot be measured or segmented with confidence.

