2.2. Study Endpoints

2.2.1. Primary Endpoint:

- Objective radiographic response (ORR), as measured by modified Response Assessment in Neuro-Oncology (RANO) criteria

2.2.2. Secondary Endpoints:

- Safety and tolerability will be assessed by monitoring frequency, duration, and severity of adverse events (AEs) through physical examinations, by evaluating changes in vital signs, and through clinical laboratory evaluations.
- OS, defined as the time from date of enrollment until death from any cause
- PFS, defined as the time from date of enrollment until the earliest date of disease progression (as determined by modified RANO criteria) or death due to any cause

2.2.3 Exploratory Endpoints:

- Comparison of the following immunocorrelative assays in subjects treated with INCMGA00012 + INCAGN01876, with or without SRS:
 - Multiplex immunohistochemistry on tumor tissue for CD4/8 T cell infiltration, Foxp3+ Treg infiltration, and PD-1/PD-L1 expression
 - Tumor cell and immune cell GITR expression by a validated immunohistochemistry stain
 - Flow cytometry/mass cytometry in tumor tissue and peripheral blood for T cell and monocyte phenotyping
 - RNA-Seq on tumor tissue for PD-1/PD-L1 and GITR expression, T cell- and interferon- γ -related gene expression, and cell-cycle-related gene expression
 - T cell receptor sequencing in tumor tissue and peripheral blood for assessment of TCR clonal diversity
- Association between the above tumor tissue and peripheral blood-based markers of immune activation, tumor genetic mutations, and clinical outcomes of OS, PFS, and ORR
- PK parameters for INCAGN01876 in patients with glioblastoma
- Detection of anti-drug antibodies (ADA) against INCAGN01876

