In both surgical sub-arms, within 7 days of enrollment the subject will receive a single dose of the investigational systemic agent(s) according to the sub-arm to which he/she is assigned. In sub-arm # 1 (INCMAG00012 + INCAGN01876 + SRS), within 3 to 7 days following the neoadjuvant doses of the systemic study drugs, the subject will receive SRS, administered over the course of 3 consecutive business days (8 Gy x 3 fractions, one fraction per day, total dose 24 Gy). Subjects may receive 3 fractions every other day (non-consecutively) for logistical reasons relating to COVID-19. Within 7-14 days following administration of the study drug(s) (surgical sub-arms # 2) or within 7-14 days following SRS (surgical sub-arm # 1), the subject will undergo maximal safe surgical resection of the tumor. Following surgery, the subject will then resume systemic therapy with BOTH investigational agents INCMGA00012 and INCAGN01876 (regardless of which of the two sub-arms the subject was assigned to). The systemic agents should be started as soon as the investigator feels the subject has recovered adequately from surgery, but must be restarted within 5 weeks (35 days) from the date of surgery. Subjects will continue on combined systemic treatment (INCMGA00012 500 mg IV every 4 weeks and INCAGN01876 300mg IV every 2 weeks) until disease progression, unacceptable AEs, or for 2 years, whichever occurs first.

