 - Exception: If subject meets radiographic criteria for PD but then undergoes a surgical resection of the area of radiographic PD per their treating oncologist's recommendation, the patient may stay on study and resume study drugs postoperatively if (i) histopathology from this surgery demonstrates only therapy-related changes and no viable tumor (scattered/rare atypical glial cells only would not count as viable tumor) AND (ii) there are no other, separate sites of PD on the immediate post-operative MRI.
 - Exception: If radiologic imaging *within the first 6 months* from the first dose of immunotherapy shows confirmed PD by mRANO criteria, participants not experiencing significant clinical decline may be allowed to continue study treatment for up to 3 months from the time of the scan showing confirmed PD. It is at the discretion of the treating physician whether to continue a participant on study treatment for up to 3 months pending confirmation of PD on follow-up imaging. This clinical judgment decision should be based on the participant's overall clinical condition, including performance status, clinical symptoms, and laboratory data. Subjects may receive study treatment while waiting for confirmation of PD if they are not experiencing significant clinical decline and if:
 - the subject is believed to demonstrate clinical benefit from the study regimen as determined by the treating physician;
 - the subject is adequately tolerating study therapy
- The study is terminated by the Sponsor.
- The IRB withdraws approval for the study

- Any progression or recurrence of any malignancy, or any occurrence of another malignancy that requires active treatment
- Occurrence of any AE that is related to either study drug that, in the judgment of the Investigator and/or Medical Director, compromises the subject's ability to continue study-specific procedures or is considered to not be in the subject's best interest.

A subject **may** be permanently discontinued from BOTH study drugs (INCMGA00012 and INCAGN01876) as follows:

- If, during the course of the study, a subject is found not to have met eligibility criteria, the medical monitor, in collaboration with the investigator, will determine whether the subject should be withdrawn from the study.
- If a subject is noncompliant with study procedures or study treatment in the investigator's opinion, the sponsor should be consulted for instruction on handling the subject.

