Adverse Event / Unanticipated Problems Assessment (Section 7)	X	X		X	X	X		X	X	X	X	X		X
INCMGA00012 Administration (Section 5)		X††				X			X		X			
INCAGN01876 Administration (Section 5)		X††				X		X	X	X	X	X		
MRI brain (tumor assessment by mRANO criteria) (Section 7)	X												X*	X†††
SRS planning** (Section 5)	X													
SRS delivery** (Section 5)			X											
Surgical Resection; tissue for correlatives (Section 7)				X										

* MRI scan should be performed within 7 days prior to the cycle start (and ideally within 3 days prior). Adjustments to this 7-day window are allowable per the treating physician’s discretion; however restaging scans MUST BE performed and reviewed before the subsequent cycle’s dose may be initiated

**SRS delivery: Total 24 Gy delivered over 3 consecutive days (8 Gy per day). Subjects may receive 3 fractions every other day (non-consecutively) for logistical reasons relating to COVID-19. Must start between 3 and 7 days after first dose of study drugs

*** PK samples for INCAGN01876 collected pre-dose and at end of infusion on Cycle 1 Day 1 and Cycle 3 Day 15. All other PK draws for INCAGN01876 are pre-dose.

† After the first 2 cycles, PK samples for INCAGN01876 are drawn only on Cycle 3 Day 15, Cycle 4 Day 1, Cycle 4 Day 15, and then only on day 15 of each cycle starting with Cycle 5

†† For the neoadjuvant dose(s) of study drugs INCMGA00012 and INCAGN01876, the subject will be assigned to receive the combination of INCMGA00012 and INCAGN01876, or the combination of INCMGA00012 and INCAGN01876 plus SRS. After surgery ALL subjects will resume the combination of both INCMGA00012 and INCAGN01876

††† MRI and mRANO assessment at EOT are only necessary if this has not already been performed within 28 days of the EOT visit
§ EOT visit occurs within 14 days from when the subject is taken off study

Table 10: Schedule of study procedures, FOLLOW-UP			
Procedure	Safety visit	Safety follow-up	Disease Status and Survival
	30 d after EOT (+/- 7 d)	12 W (+/-14 d) after EOT	Q12W after EOT (+/- 14d)
Karnofsky Performance Status (Section 7)	X		
Targeted Physical Assessment (Section 7)	X		
Vital Signs: BP, HR, RR, weight (Section 7)	X		
Prior/Concomitant Medications (Section 7)	X	X	
Clinical Laboratory Evaluation (CBC, CMP, Mag, Phos, LDH) (Section 7)	X		
Urinalysis (Section 7)	X		
Clinical laboratory Evaluation – endocrine (TSH, T4) (Section 7)	X		
Urine Pregnancy Test (Section 7)	X		

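### Cohort B response is scored against the pre-operative scan, so tumour removed by surgery can count towards PR or CR, and no post-operative reference MRI is scheduled

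*Combined protocol and SAP*

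**What the plan says.** Section 7.7.1 gives the reference for response: "Radiologic response will be assessed by comparing the pretreatment baseline and on-treatment MRI scans". For progression it says: "Radiologic progression will be determined by using the smallest tumor measurement at either the pretreatment baseline or after initiation of study medication". It also fixes the imaging interval: "MRI scans will be performed no less frequently than every 8 weeks". None of these rules has a Cohort B variant, in Section 7.7 or in Section 8.

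Section 3.1.2 places surgery after the pretreatment scan and after the neoadjuvant treatment. The timing is "Within 7-14 days following administration of the study drug(s) (surgical sub-arms # 2) or within 7-14 days following SRS (surgical sub-arm # 1"), and at that point "the subject will undergo maximal safe surgical resection of the tumor". Both study drugs must then be restarted within 35 days of surgery.

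In Table 9 (Section 6, Cohort B), the row "MRI brain (tumor assessment by mRANO criteria) (Section 7") is marked at screening, in the 8-weekly column before odd cycles, and at end of treatment. The Pre-Op, Post-Op and Cycle 1 columns are blank.

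Section 7.7.2 requires for PR a fall of at least 50% from baseline, held for at least 4 weeks. CR requires all enhancement to be gone for the same period. Both also carry new-lesion, T2/FLAIR, steroid and clinical conditions.

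Among the exploratory endpoints, Section 2.2.3 lists "Association between the above tumor tissue and peripheral blood-based markers of immune activation, tumor genetic mutations, and clinical outcomes of OS, PFS, and ORR".

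**The concern.** A response endpoint should measure what treatment does to tumour that is present. In Cohort B the reference lesion is measured, treated once before surgery, and then removed as far as is safe. Compared with the pre-operative scan, the fall in size combines extent of resection with any drug or SRS effect, and nothing in the definitions separates the two.

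The tissue-marker work is where this matters most. The only tumour tissue that the protocol schedules for collection during treatment is the Cohort B resection specimen (Section 7.9). If response in those subjects partly reflects how much the surgeon could remove, a marker could appear to predict response, or fail to, for reasons unrelated to the drugs.

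A second, lesser issue concerns PFS. With no scheduled scan between surgery and Cycle 3, size-based progression has no scheduled post-operative reference until that first on-treatment scan.

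**Working it through.** **1. Can resection alone meet the size criterion?** Let f be the fraction of the enhancing bidimensional product removed, with no drug effect. The residual is (1 − f) × baseline. PR size is met when (1 − f) × growth ≤ 0.50, so the residual stays PR-sized until it has grown 0.50/(1 − f)-fold. If the pre-operative size is still the smallest measurement before the scan in question, size-based PD needs 1.25/(1 − f)-fold growth. The documents do not give f, so a range is assumed:

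| f (assumed) | Residual | Still PR-sized until growth of | Size-based PD at growth of |
|---|---|---|---|
| 50% | 50% | 1.0-fold (at the limit) | 2.5-fold |
| 80% | 20% | 2.5-fold | 6.25-fold |
| 90% | 10% | 5-fold | 12.5-fold |

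Against a post-operative reference, PD is reached at 1.25-fold for any f that leaves measurable residual, and PR needs the residual itself to halve. Resection alone then cannot give PR.

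**2. Does the confirmation rule remove the problem?** No, because resected tumour stays absent, but it does raise the hurdle. Table 9 has no 4-week confirmation scan. With restart 35 days after surgery, the first scheduled scan falls 35 + 56 − 7 = 84 to 35 + 56 = 91 days after surgery, and the next 56 days later, at 140 to 147 days. With restart at day 14 (assumed), the two fall at 63–70 and 119–126 days. Unless an unscheduled scan confirms earlier, the tumour must be at or below half its pre-operative size at both scans, the second about 17 to 21 weeks after surgery (119/7 to 147/7).

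**3. Is the first on-treatment MRI really before Cycle 3?** Yes. In Table 9, thyroid tests and correlative blood are marked at Cycle 1 and again in the 8-weekly column, so that column does not cover Cycle 1. MRI is marked only in the 8-weekly column.

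**4. Length of the gap.** The stated maximum is 8 weeks = 56 days. It reproduces in Cohort A when counted from first dose: Cycle 1 Day 1 to Cycle 3 Day 1 is 56 days. For Cohort B, counted from the screening MRI and ignoring the ±2-day visit windows and weekends:

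- Sub-arm 1, maximum: 14 (screening to dose) + 7 (to SRS) + 4 (three alternate-day fractions) + 14 (to surgery) + 35 (to restart) + 56 = 130 days. With consecutive fractions it is 128.
- Sub-arm 2, maximum: 14 + 14 + 35 + 56 = 119 days.
- Sub-arm 1, minimum: 0 + 3 + 2 + 7 + 0 + 56 − 7 = 61 days. Sub-arm 2, minimum: 0 + 7 + 0 + 56 − 7 = 56 days. Both assume no recovery time after surgery.

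The same screening count gives Cohort A up to 14 + 56 = 70 days, so part of the excess is common to both cohorts. Counted from first dose, the Cohort B maxima are 130 − 14 = 116 and 119 − 14 = 105 days, against 56 in Cohort A.

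**5. Reach.** Section 8.1 limits the primary analysis to Cohort A. Its design reproduces: with N = 16, three or more responders gives one-sided alpha 0.0429 at 5% and power 0.803 at 25%. Nothing here changes that.

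**The case against.** The strongest reply is that little rests on Cohort B response. The cohort is exploratory, its efficacy results are descriptive, the secondary efficacy endpoints are OS and PFS, and Section 8.2.2 specifies no Cohort B ORR analysis. That stands and limits the importance of the point. It does not remove it, because ORR is named in the biomarker association and the synopsis foresees descriptive Cohort B efficacy.

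A reader might infer that most of the 16 subjects would be scored as responders through surgery. The documents do not support that. Extent of resection is not given. Section 4.1 lets sub-arm 2 enrol any tumour size without requiring measurable disease. The steroid, T2/FLAIR, new-lesion and clinical conditions must also hold, and a steroid increase within 2 weeks of a scan makes that time point non-evaluable.

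A reader might also infer that early regrowth goes unseen. That too is more than the text supports: clinical deterioration, a new enhancing measurable lesion, clear progression of non-measurable disease or failure to return because of decline each give PD, and unscheduled assessments are foreseen. What is missing is a scheduled scan.

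Finally, it can be said that a post-operative MRI is routine, and that Section 7.7.1 already counts any measurement after study drug starts towards the progression nadir. The nadir point is right. Response would still be scored against the pre-operative scan. The one post-operative MRI that the protocol mentions ("there are no other, separate sites of PD on the immediate post-operative MRI", Section 5.7) belongs to resection of an area of on-study progression, not to the planned surgery, and Section 5.10 names no scan.

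**Conclusion.** The point holds as a flaw in a stated rule. As written, a Cohort B subject whose enhancing tumour remains at or below half its pre-operative size because of surgery can be scored PR, or CR if no enhancement remains, when the other Section 7.7.2 conditions are met. The number affected cannot be derived; the growth figures rest on assumed resection fractions and no drug effect.

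The descriptive Cohort B ORR and the tissue-marker association with ORR are affected directly. Cohort B PFS, its marker associations and the exploratory log-rank test between cohorts are affected only through the missing scheduled reference scan. It would be wrong to say that PFS inherits the same error as ORR, or that the primary result is at risk.

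The interval contradiction is real. The gaps of 130 and 119 days, and of 91 days after surgery, require every relevant window at its maximum and the scan on Cycle 3 Day 1. In sub-arm 1, even the shortest count (61 days) exceeds 56.

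**What to change.** - For Cohort B, do not report ORR against the pre-operative scan, and do not use it in the biomarker–ORR association.
- Where routine care provides a post-operative MRI before Cycle 1, name it as the Cohort B response reference and score response only in subjects with measurable residual disease on it. State explicitly that it also counts for the progression nadir, as Section 7.7.1 already allows.
- Reconcile Table 9 with the 8-week statement in Section 7.7.1. Naming a reference does not settle this by itself: a scan taken immediately after surgery can still precede the next scheduled one by up to 91 days. A scan 0 to 7 days before Cycle 1 Day 1 would leave 49 to 63 days (56 − 7 to 56 + 7).

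The first two changes are wording only. The cost is fewer Cohort B subjects evaluable for response, possibly few enough that only a listing is sensible. That a routine post-operative MRI will be available is an assumption; where there is none, Cohort B response should be left unscored. Cohort A's sample size and power do not change.
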